12.4 Missing Values and Model Violations

The possibility of bias from missing data of subjects who prematurely discontinue for reasons possibly related to study drug will be addressed. If it is concluded that there may be a bias of meaningful magnitude as a result of premature discontinuation, a value may be imputed for the missing pharmacokinetic parameter or missing concentrations, Sensitivity analyses might be carried out with the missing value replaced over a range of values.

In some cases of a missing individual concentration value, values of pharmacokinetic variables (C_{max} , AUC, etc.) will be determined without replacing missing individual concentration values, but simply using the available data. However, if a missing individual concentration value results in a value of a pharmacokinetic parameter that may be too low or too high to a meaningful degree, the value of the pharmacokinetic parameter will tentatively be considered missing. In this case, a value for the missing individual concentration may be imputed so that an appropriate value of the pharmacokinetic parameter can be included in the analysis. The imputed value will be obtained using appropriate methodology that takes into account the individual characteristics of the subject. Also, if the concentration value at the beginning or end of the dose interval is missing, a value must be imputed in order for a value of AUC to be determined.

An imputed value will be obtained using appropriate methodology that takes into account the individual characteristics of the subject. The data set from which the value is imputed will be restricted to that of subjects whose data could be considered a random sample from the probability distribution applicable to the subject with the missing data. Ordinarily, the data set from which the imputed value is obtained would be that of the treatment group to which the subject with the missing value is a member, or some

appropriate subset of the treatment group, using only subjects who do not have missing values of their own that would make them unsuitable for the purpose.

As stated in Section 12.4, it is expected that the logarithmic transformation will be used for dose-normalized AUC and dose-normalized C_{\max} and is likely to be used for pre-infusion concentration (or C_{trough}). The primary purpose of a transformation will be to have a random variable with an approximately symmetric probability distribution, but an approximately symmetric distribution with apparently very heavy tails (e.g., kurtosis coefficient, as defined in the SAS Procedure Univariate, exceeding 9) would also be of concern. If an adequate transformation is not found for a variable, then a non-parametric analysis may be performed.

13.0 Analysis of Biomarker Research Variables

Descriptive Statistics

Descriptive statistics will be provided for each variable by treatment and scheduled time of measurement. The statistics will consist of: number of observations (n), mean, standard deviation, coefficient of variation as a percentage (quotient of standard deviation and mean, multiplied by 100), minimum, median and maximum. If the logarithmic transformation is employed for the analysis of a variable, the geometric mean will also be reported.

Transformation of Variables for Analysis

If the probability distribution for a variable appears to have considerable non-symmetry (e.g., skewness coefficient > 1.00 in magnitude), a transformation will be sought that has an approximately normal distribution. If a transformation is employed for the analysis, estimates of central values on the original scale (back transformation of SAS least squares means) will be provided. If the logarithmic transformation is used, the comparison of a pair of treatments (usually with placebo as the reference treatment) will be in terms of the ratio of central values.

Analysis of CSF Concentration Variables

An ANCOVA model will be used to evaluate CSF concentrations for total tau, free tau and the ratio of free tau concentration to total tau concentration for each scheduled time of evaluation during treatment (fourth dose interval and Week 96). For the analysis for the fourth dose interval, an analysis will be performed for the data of Cohort 1 alone and also for all available data. The observations will be classified by treatment. The baseline value for total tau and free tau (last value before the first dose of study drug) will be the covariate in the case of total tau and free tau, but for the analysis on the ratio the covariate will be the baseline total tau concentration measurement. If the probability distribution for a variable appears to have considerable non-symmetry (skewness coefficient > 0.75 in magnitude), a transformation will be sought so that the transformed variable has an approximately normal distribution. For each ABBV-8E12 dose level, the results of the test of the hypothesis of no difference between the dose and placebo will be reported. Also, with the motivation to have a test with good power if the dose response curve is a monotonic function of dose, a test will be performed on a contrast in the four treatment means. With μ_0 , μ_1 , μ_2 and μ_3 denoting the means for placebo, the 300 mg treatment, the 1000 mg treatment and 2000 mg treatment, respectively, the hypothesis that $-3\mu_0 - \mu_1 + \mu_2 + 3\mu_3 = 0$ will be tested at significance level 0.050 against the two-sided alternative hypothesis. The tests on the effects of the 1000 mg dose and the 300 mg dose will not be formally considered unless the statistic on the effect of the 2000 mg dose or the statistic on the contrast in the four means is significant at level 0.050.

CSF NFL concentration will be analyzed as described above for CSF total tau concentration. The same will be done for other CSF concentration variables for which data are reported, provided that the proportion of measurements that are outside the limits of quantification and the magnitude of the lower limit do not make a conventional analysis of covariance inappropriate.

Analysis of Serum/Plasma Concentration Variables

An analysis will be performed for plasma total tau concentration and for plasma NFL concentration. If the data are reported for other plasma concentration variables, an analysis like that described for plasma total tau concentration will be performed, provided that the proportion of measurements that are outside the limits of quantification and the magnitude of the lower limit do not make the methodology inappropriate.

A MMRM analysis will be performed on the data from scheduled times of measurement. The model will include the baseline value as a covariate, have classification of subjects by treatment, an effect for time (classification) and will include an effect for the interaction of treatment and time of measurement. The initial model will also allow the regression coefficient for the baseline value to vary with time (an effect for interaction of time and the baseline value), but this feature will be removed from the model if the statistic on this interaction is not significant at level 0.100. The subjects of each treatment group will be viewed as a random sample, and an appropriate structure for the covariance matrix of the measurements of a subject will be selected. Within the framework of this model, the mean across the scheduled times of measurement will be estimated for each treatment. Also, tests on differences of effect among the dose levels (with placebo considered a dose level) will be performed within the framework of the model. Tests on the dose level main effects will be performed as described for dose level effects in the analysis of covariance for CSF free tau concentration and CSF total tau concentration. These same tests will be provided for each time of measurement in the framework of the MMRM model, and the tests for the individual times will be given the greater attention if the statistic on the interaction of treatment and time of measurement is significant at level 0.100.

Analysis of Volumetric MRI Variables

For volumetric MRI variables, descriptive statistics will be provided for the baseline value, for each scheduled time after that and for the changes from baseline. An MMRM analysis will be performed like that described for plasma NFL concentration, but with an additional covariate, estimated total intracranial volume (eTIV), in the model. The

regression coefficient for eTIV will not vary with time, as may be allowed for the vMRI baseline value.

Analysis of Tau PET Scan Variables

For each region of the brain for which SUVR values are obtained, a joint analysis will be performed for the two scheduled times of evaluation during treatment (Week 44 and Week 96). The analysis will be like that described for plasma NFL concentration with some additional assumptions made. The model will be that of a MMRM analysis even though there are only two times of measurement. The baseline value will be a covariate, with the regression coefficient assumed to be the same for the two times of measurement. Compound symmetry will be assumed for the covariance matrix of the error terms of the two times of measurement. If data are reported for other continuous variables that reflect the extent of tau pathology, a similar approach will be used for their analysis.

Consideration of Premature Discontinuations

The possibility of bias from missing data of subjects who prematurely discontinue for reasons possibly related to study drug will be addressed. If it is concluded that there may be a bias of meaningful magnitude as a result of premature discontinuation, sensitivity analyses may be carried out. Also, some imputation of missing values for subjects who prematurely discontinue might be done.

Relationship with Disease State

For some of the exploratory biomarker variables, an analysis will be performed to explore the relationship to disease state/progression. Disease state will be represented by CDR-SB score, and explorations may be carried out on the relationship between the biomarker variables and other measures of disease level. The biomarker variables will include, but not necessarily be limited to, plasma total tau concentration, plasma NFL concentration, and the vMRI measures for whole brain, hippocampus, temporal lobe and lateral ventricles. The relationship between change in CDR-SB score and change in biomarker will be explored.

The schedule of visits for which the biomarker measurements are obtained are not the same as the schedule of visits on which the CDR-SB assessments are done. For plasma concentration variables and vMRI variables, respectively, the visits defining the bivariate observations composing the data sets on which the analyses will be performed are shown in the two tables that follow. Although there were times of evaluation before Week 48 for both plasma concentration biomarkers and CDR-SB, there was no pair of visits before Week 48 for which the blood sample for the biomarkers and the CDR-SB evaluation were judged to be close enough in time to form an acceptable bivariate observation.

Bivariate Observations for CDR-SB and Plasma Concentration Variable		
Observation	Visit for CDR-SB Score	Visit for Plasma Concentration
1	Week 48	Week 48
2	Week 72	Week 72
3	Week 96	Week 96

Bivariate Observations for CDR-SB and vMRI		
Observation	Visit for CDR-SB Score	Visit for vMRI Measurement
1	Week 24	Week 28
2	Week 48	Week 44
3	Week 72	Week 68
4	Week 96	Week 96

For each biomarker variable, the bivariate data of CDR-SB and the biomarker variable for each combination of treatment and time of observation will be plotted. With each plot Spearman's rank correlation coefficient and the p-value for the test of independence will be provided. An investigation of the relationship of CDR-SB with the biomarker variable for all of the times of observation jointly will be carried out in the framework of a MMRM analysis with decrease from baseline in CDR-SB score as the response variable and with change from baseline in the biomarker variable as a covariate (explanatory variable) that changes with time. If a transformation is used for the analysis of the biomarker variable itself, that same transformation will be used for the biomarker variable in this analysis; that is, the covariate will be the change from baseline in the value of the

transformed variable. The model will include classification by time of observation, which can also be thought of as the visit at which the CDR-SB evaluation was done. The model will include classification by treatment and the interaction of treatment and time. The initial model will have interaction of the covariate with treatment, allowing the regression coefficient of the covariate to depend upon treatment. This interaction effect will be removed from the model if the statistic on the interaction is not significant at level 0.100 in the analysis with the final choice of the structure for the covariance matrix of the error term, as discussed in the paragraph that follows.

The initial model will impose no restrictions on the covariance matrix for the error term (using Option UN with the SAS REPEATED statement). A simpler structure for the covariance matrix will be considered, with the correlation coefficients for all pairs of times assumed to be the same while imposing no restrictions on the variances for the several times (using Option CSH with the SAS REPEATED statement). An approximate test of the hypothesis that the covariance matrix with the more complex model is same as the covariance matrix with the simpler model will be performed. The approximate test will be that based upon the difference in the values of $-2\log(\text{likelihood})$ for the two models, using the chi-square approximation for the null distribution, with degrees of freedom being the difference in the number of parameters required for the two structures of the covariance matrix. If the test statistic is not significant at level 0.050, the simpler model will be tentatively adopted. In that case, the compound symmetry structure (default option with the SAS REPEATED statement) will be considered. The approximate test for the comparison of the two models will again be performed. The compound symmetry model will be adopted only if the test statistic is not significant at level 0.050. If the computational algorithm does not satisfactorily converge with a particular structure assumed for the covariance matrix, that structure will not be adopted, and only the simpler structure(s) will be considered.

If the final model contains an effect for the interaction of treatment and covariate, the estimate for each of the four regression coefficients and for the average of the four regression coefficients will be provided. For each of the four regression coefficients

and for their average, a two-tailed test of the hypothesis that the regression coefficient (or the average) = 0 will be performed at significance level 0.050. This will serve as a test of the hypothesis that the correlation coefficient between the CDR-SB change from baseline and the biomarker change from baseline is 0. If the final model does not contain an effect for the interaction of treatment and covariate (a common regression coefficient for all four treatments), this hypothesis test will be performed on the single regression coefficient and will apply to placebo and all three ABBV-8E12 treatments.

To give further confidence in the assessment of the relationship of the biomarker variables with disease state and progression in the absence of treatment with ABBV-8E12, a MMRM analysis will be performed on the data set restricted to subjects on the placebo treatment. The model and analysis will be simpler than that described above in that there will be no effects involving treatment. In particular, there will be only a single regression coefficient.

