
Objectives:
 
The primary objectives of this study are:
 
 To assess the efficacy of ABBV-8E12 in slowing disease progression (cognitive and functional impairment) in subjects with Early Alzheimer's Disease (AD) as measured by the Clinical Dementia Rating – Sum of Boxes (CDR-SB). To assess the long-term safety of ABBV-8E12 for up to 96 weeks in subjects with Early AD. 
The secondary objectives of this study are:
 
 To assess the pharmacokinetics of ABBV-8E12 in subjects with Early AD. To assess the efficacy of ABBV-8E12 in slowing cognitive and functional impairment in subjects with Early AD as measured by the Mini-Mental State Examination (MMSE), Alzheimer's Disease Assessment Scale (14-Item) Cognition Portion (ADAS-Cog-14), Repeatable Battery for Assessment of Neuropsychological Status (RBANS), 24-Item Alzheimer's Disease Cooperative Study/Activities of Daily Living Scale Adapted for Patients with Mild Cognitive Impairment (ADCS-MCI-ADL-24), Functional Activities Questionnaire (FAQ) and University of California San Diego Performance Based Skills Assessment, Brief Version (UPSA-Brief). To assess the global impact of ABBV-8E12 on cognition, function and behavior as measured by Alzheimer's Disease Cooperative Study Clinical Global Impression of Change for Mild Cognitive Impairment (ADCS-CGIC-MCI). 
The exploratory objectives of this study are:
 
 To assess the effect of ABBV-8E12 on cerebrospinal fluid (CSF) and plasma tau protein. To assess the effect of ABBV-8E12 on potential CSF and plasma biomarkers of disease progression. To assess the efficacy of ABBV-8E12 in slowing the rate of regional and/or whole brain atrophy in subjects with Early AD as measured by volumetric magnetic resonance imaging (vMRI). To assess any signals or trends for efficacy of ABBV-8E12 in removing tau deposits or slowing the accumulation and spread of tau deposits in the brain as measured by tau positron emission tomography (PET) in a subset of subjects. To generate additional data for the correlation between retinal amyloid imaging and amyloid PET imaging in a subset of subjects. To characterize the performance of a digital clock drawing test (dCDT) in measuring cognitive function and assess its correlation with other clinical rating scales and biomarkers in a subset of subjects. 	

Investigators: Multicenter
Study Sites: Up to 80 global sites

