5.3.6 Biomarker and Pharmacogenetic Research Variables

5.3.6.1 Biomarker Research Variables

CSF and Plasma Concentration Variables

CSF samples will be assayed for neurofilament light chain (NFL), free tau and total tau, and the ratio of free tau concentration to total tau concentration will also be statistically analyzed. The assessments on free tau and the ratio of free tau to total tau will be done to investigate the binding of ABBV-8E12 to CSF tau. Plasma samples will be assayed for tau and NFL to understand the relationship to disease progression and response to treatment. Plasma samples may also be analyzed for plasma Abeta 40 and Abeta 42 to study relationship with amyloid PET positivity.

CSF and blood samples may be analyzed for biochemical or macromolecular factors (e.g., amyloid beta) related to the pharmacodynamics and safety of ABBV-8E12. Additional CSF, plasma and/or serum evaluations may include analyzing biomarkers related to the pathway(s) targeted by the study drug or believed to be related to the disease or to drug response. Biomarker samples may also be used for non-genetic exploratory research to assess and generate prognostic, predictive, pharmacodynamic, or surrogate biomarker signatures or develop assays. In addition, the information learned from analyzing these samples may be used to investigate factors impacting response to treatment, scientific questions related to various disease where ABBV-8E12 may be investigated, or in the development of new therapies. The results of biomarker testing may not be reported in the clinical study report.

Volumetric MRI

Baseline vMRI measurements and measurements on change from baseline in vMRI measurements for MRIs from Week 28 through Week 96 will be obtained. Measurements will be obtained for whole brain, hippocampus and lateral ventricles. Measurements may be obtained for additional regions.

Tau PET Imaging

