Descriptive statistics will be provided for plasma concentrations of total tau and NFL. For each of these variables, an MMRM analysis will be performed on the data from the scheduled times of measurement. The model will include the baseline value as a covariate, have classification of subjects by treatment, an effect for time (classification) and will include an effect for the interaction of treatment and time of measurement. The initial model will also allow the regression coefficient for the baseline value to vary with time (an effect for interaction of time and the baseline value), but this feature will be

removed from the model if the statistic on this interaction is not significant at level 0.100. Within the framework of this model, the mean across the scheduled times of measurement and the mean for each individual time will be estimated for each treatment. Also, tests on differences of effect among the dose levels (with placebo considered a dose level) will be performed within the framework of the model. The primary tests will be on trend with dose (with placebo considered a dose level) and on the difference between the highest dose and placebo.

For total tau and NFL, the relationship to disease progression and response to treatment will be explored with disease state represented by CDR-SB score and perhaps by other variables of interest. The exploration on the relationship with disease progression will include an analysis of data from only the subjects treated with placebo.

Descriptive statistics and some or all of the analyses described here may be provided for other variables.

vMRI Variables

Descriptive statistics will be provided for the baseline value, for each scheduled time after that and for the changes from baseline. An analysis will be performed like that described for plasma NFL concentration, but with estimated total intracranial volume (eTIV) as a covariate in addition to the baseline value. The regression coefficient for eTIV will not vary with time, as may be allowed for the vMRI baseline value. An appropriate structure for the covariance matrix will be selected.

For each of whole brain, hippocampus and lateral ventricles, the relationship with the primary efficacy variable CDR-SB score, and possibly other efficacy variables, will be explored. The exploration will include an analysis of data from only the subjects treated with placebo. This may also be done for other regions.

Tau PET Scan Variables

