5.1 Variables Used for Stratification of Randomization

Subject randomization is stratified by study site.

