10.2 Primary Analysis of Primary Efficacy Endpoint

The primary efficacy endpoint is the change from baseline to Week 96 visit on the CDR--SB score. The primary analysis population will be subjects in the ITT dataset and the primary analysis will be a likelihood-based, mixed-effects model, repeated measures (MMRM) analysis of the change from baseline to each post-baseline assessment up to and including Week 96. The model will include fixed, categorical effects for treatment, site, visit, baseline score-by-visit and treatment-by-visit interactions, with continuous fixed covariate for baseline score. The primary comparison will be the contrast between each ABBV-8E12 dose group and placebo group at Week 96. Contrasts between each ABBV-8E12 dose group and placebo at Weeks 24, 48, 72, and overall across the treatment period will be obtained and will be considered as secondary. An unstructured (co)variance structure will be used to model the within-patient errors. The same (co)variance structure will also be used for all MMRM analyses for secondary efficacy variables. Satterthwaite's approximation will be used to estimate denominator degrees of freedom.

The following statistics will be presented on the statistical table of MMRM analysis for change from baseline to each visit (Weeks 24, 48, 72, and 96): descriptive statistics

(number of non-missing observations, mean, standard deviation, minimum and maximum) for each treatment group. Within group LS mean and standard error will be presented for each treatment group. LS mean, standard error, 95% confidence interval and two-sided *P* values for comparisons between each ABBV-8E12 dose group and placebo at each post-baseline visit will also be presented. The LS mean, standard error, 95% confidence interval and two-sided *P* values of treatment difference comparing each ABBV-8E12 dose group with placebo across the treatment period will be included in the output as well.

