10.5 Combination of Sites with Fewer than 2 Subjects per Treatment Group

When "site" is included as a factor in a statistical model, sites that do not have at least 2 subjects per treatment group for the ITT dataset will be combined within each country as follows.

1. Divide the sites into 2 groups with Group 1 including all sites that have at least 2 subjects per treatment group and Group 2 including all remaining sites. Sort each group in ascending order by total sample size and investigator number.

2. Starting at the top of the Group 2 list (i.e., the first site with the smallest sample size), combine the minimum number of sites required to achieve a pseudo-site that has at least 2 subjects per treatment group. Continue this process until all Group 2 sites have been grouped into pseudo-sites.
3. If there is a site (or sites) left after Step 2, combine this site (or sites) with the last pseudo-site that is created. For the situation where there is no previous pseudo-site exists, combine this site (or sites) with the first site on the sorted Group 1 list.

The naming of the pseudo-sites will be given by xxx99901, xxx99902, etc., where xxx is the country code.

The combined pseudo-sites will be used in all statistical models that include the "Site" as a factor. However, the original site identification will be used in all summaries of subject disposition or discontinuation by Study Site and in all data listings. In the summaries of the number and percentage of subjects contributed by each site in each treatment group for the ITT dataset, the name of pseudo-sites will also be displayed.

10.6 Handling of Missing Data for Efficacy Assessments and Sensitivity Analysis of the Primary Efficacy Endpoint

Missing Items for a Rating Scale

Unless otherwise specified, when an efficacy variable is a total score calculated from a set of individual items, the total score will be considered missing if any of the individual items are missing.

Missing Visit Data

Before conducting any imputation of missing data, patterns of missing data for the primary endpoint CDR-SB score in placebo and three ABBV-8E12 arms will be assessed. Observed mean changes from baseline in CDR-SB score will be summarized over time for different missing patterns of longitudinal data (discontinued before Week 24 assessment, discontinued after Week 24 assessment, discontinued after Week 48

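### The exploratory plasma tau, plasma NFL and volumetric MRI models leave out site, the only stratification factor; a random site intercept would recover a little precision at almost no cost

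*SAP*

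**What the plan says.** SAP 5.1 names one stratification factor: "Subject randomization is stratified by study site". Protocol 8.3 agrees.

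The primary CDR-SB model in SAP 10.2 uses that factor: "The model will include fixed, categorical effects for treatment, site, visit, baseline score-by-visit and treatment-by-visit interactions". SAP 10.3.1 carries it into the secondary efficacy MMRMs. In these models a small site is not its own level. Under SAP 10.5, "sites that do not have at least 2 subjects per treatment group for the ITT dataset will be combined within each country", and the resulting pseudo-sites are to be used wherever site is a model factor.

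The biomarker models in SAP 13.0 differ. For plasma total tau and NFL the MMRM specification begins "The model will include the baseline value as a covariate, have classification of subjects by treatment, an effect for time (classification"; treatment-by-time follows and, unless dropped at the 0.100 level, baseline-by-time. Protocol 8.1.5 lists the same terms: "have classification of subjects by treatment, an effect for time (classification) and will include an effect for the interaction of treatment and time of measurement". For vMRI the model is built on it: "An MMRM analysis will be performed like that described for plasma NFL concentration, but with an additional covariate, estimated total intracranial volume (eTIV". Neither has a site or scanner term, and neither document says why the factor kept for the clinical scales is dropped here. The CSF ANCOVA and the tau PET model omit it as well.

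Plasma tau, plasma NFL and vMRI come under the exploratory objectives (Protocol 4.0, SAP 4.1) and lie outside the family-wise error control of SAP 10.7.

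**The concern.** When randomisation is balanced within site, the variance of the treatment contrast is already lower to the extent that sites differ in outcome. A model that ignores site does not credit this reduction, so its standard errors are too large and its tests conservative.

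Sites could plausibly differ in measured change. Missed MRIs and blood samples are deferred to the next onsite visit (Protocol 5.3.1.1 and 5.3.1.2). Home visits are offered only where local rules allow (Protocol 5.5.1). SAP version 3.0 removed the analysis windows for vMRI and NFL (SAP 14.0). Delays that vary by site would shift follow-up values in ways that a baseline value cannot absorb. The documents do not quantify this.

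At stake is some precision in whole-trial readouts that the plan itself relates to CDR-SB. There is also a knock-on effect. The 300 mg and 1000 mg tests are formally considered only if the 2000 mg test or the trend contrast reaches 0.050, so a conservative first step can hold back the rest.

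**Working it through.** **Inputs from the documents.** 400 subjects, 1:1:1:1, 25% without post-baseline data (SAP 4.3): 100 × 0.75 = 75 per arm. "Study Sites: Up to 80 global sites" (Protocol 1.2): 400/80 = 5 subjects per site, 1.25 per arm per site. The pooling rule needs 4 × 2 = 8 subjects per level, so at most 400/8 = 50 levels.

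**Assumptions.** Residual site share of variance after baseline adjustment (ICC) from 0 to 0.20; permuted blocks of 4 within site; baseline slope 0.7 in the simulations. None is given in the documents.

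**The plan's own figure.** The only stated power, about 80%, is for CDR-SB. With 75 per arm, effect sizes 0.45, 0.45 and 0.28, and one-sided 0.025/3, the chance that at least one dose wins is 80.6% (normal) or 80.1% (t). The stated figure therefore reproduces in that sense, which supports 75 per arm as the basis below. No power is stated for the biomarker models.

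**What baseline already removes.** A stable site or scanner offset is present at baseline and at follow-up. With baseline slope b, a share (1 − b)² of its variance remains: 25% at b = 0.5, 9% at 0.7, 1% at 0.9. Site differences in change remain in full.

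**Upper bound on the gain.** If all residual site variance were removed at no cost, the SE ratio would be √(1 − ICC): 0.975, 0.949 and 0.894 at ICC 0.05, 0.10 and 0.20.

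**Fixed site effects in a realistic layout.** 1,500 simulated trials per setting; one visit, 80 unequal sites, 25% random loss, residual SD 1, 2000 mg against placebo. On average about 16 of the 80 sites met the 2-per-arm rule unaided, and about 36 groups remained after pooling (treated as one country). Mean model SE:

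| ICC | Site omitted | Fixed pooled site | Fixed, all sites | Change with pooled site |
|---|---|---|---|---|
| 0 | 0.164 | 0.168 | 0.176 | +2.4% |
| 0.05 | 0.164 | 0.165 | 0.172 | +0.8% |
| 0.10 | 0.164 | 0.162 | 0.167 | −0.9% |
| 0.20 | 0.164 | 0.157 | 0.158 | −4.1% |

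Percentages use four-decimal SEs, e.g. 0.1572/0.1639 = 0.959 at ICC 0.20. Power at 0.45 SD, omitted against pooled: 77.9/75.9%, 78.5/77.7%, 77.5/77.9% and 79.8/81.3%.

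**Is the SE without site too large?** In the two runs per setting (null and 0.45 SD), the empirical SD of the estimate with site omitted was 0.161 and 0.157 at ICC 0.10, and 0.152 and 0.153 at 0.20. The model reported 0.164 each time. Using four-decimal SDs, 0.164/0.1606 = 1.02 and 0.164/0.1569 = 1.05 at ICC 0.10; 0.164/0.1533 = 1.07 and 0.164/0.1515 = 1.08 at 0.20. So the stratified design has delivered the precision and the model does not report it. Type I error with site omitted was 5.0, 4.7, 4.7, 4.9 and 3.8% at ICC 0, 0.02, 0.05, 0.10 and 0.20.

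**Random site intercept, same layout.** The SE is essentially unchanged at ICC 0, about 4% lower at 0.10 (0.164 × 0.96 = 0.157) and about 8% lower at 0.20 (0.164 × 0.92 = 0.151). These match the empirical SDs above. In a separate set of simulated trials, power at 0.45 SD, omitted against random site, went from 76.9% to 77.3% at ICC 0, from 79.6% to 80.9% at 0.10 and from 79.6% to 84.8% at 0.20. At 0.20, type I error moved from 3.2% to 4.9%.

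Monte Carlo error in the 1,500-trial runs is about 1.1 points on power and 0.6 on type I error. Power differences near one point should not be read as real.

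**The case against.** The strongest case for leaving the models alone is this. Every one of them adjusts for a baseline value, and for vMRI the protocol plans within-subject change: "Baseline vMRI measurements and measurements on change from baseline in vMRI measurements for MRIs from Week 28 through Week 96 will be obtained". Most of a stable scanner or assay offset therefore drops out. With about 5 subjects per site, most pooled levels would mix unrelated scanners and sample handling. The fixed pooled term loses precision when the site share is small, and the documents do not say how large it is. Protocol and SAP agree on the model. The readouts are exploratory. The laboratory and MRI manuals, which may limit differences between sites, are not available here.

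Most of this stands. It rules out several stronger readings that a reader might infer:

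- That site and scanner variation stays whole in the error term. The baseline covariate removes most of any stable part.
- That omitting site biases the contrasts or inflates type I error. It does neither.
- That the SE would fall by 2.5%, 5% or 11%. Those are the cost-free upper bounds, not what this layout yields.
- That copying the efficacy models' site term would clearly help. Below a share of about 0.05 it hurts.
- That the two documents conflict. They do not.

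The objection does not defeat a random intercept. When the site variance is near zero, the estimate shrinks towards zero and the model returns close to the current one, so the cost that counts against the fixed term largely disappears.

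**Conclusion.** The point holds as a small precision improvement for exploratory analyses. The stratification factor is left out of the plasma total tau, plasma NFL and vMRI MMRMs without a stated reason. The contrasts remain unbiased, and the tests are valid to slightly conservative. With a random site effect the recoverable SE is about 0 at a residual site share of 0, 4% at 0.10 and 8% at 0.20.

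Those sizes rest on an assumed site share and on a single-visit simulation with normal data, random dropout and blocks of 4. If the share is below about 0.05, the gain is too small to notice. A reader might infer that a weak biomarker result could be blamed on this omission, or that the CDR-SB result is affected. The documents support neither: the effect on the SE is modest at most, and the primary model already includes site.

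**What to change.** In SAP 13.0, add study site as a random intercept to the plasma total tau, plasma NFL and vMRI MMRMs, keeping the other terms as they are. State that this term uses the original site and is exempt from the SAP 10.5 pooling, which would otherwise apply to any model containing site. Pre-specify that if the model fails to converge, or the site variance is estimated as zero, the current model is reported. Record the departure from Protocol 8.1.5 in SAP 14.0, before unblinding.

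The cost is a few lines of SAP text, one extra variance component and the convergence fallback. A site intercept will not capture a scanner change within a site. The smaller CSF and tau PET subsets can stay without site.
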